9.2 Secondary Efficacy Analysis

Secondary outcomes measured on a continuous scale, with a baseline measurement, will be analysed using a similar approach to that outline for the primary efficacy outcome. The data from each post-operative timepoint will be analysed in a separate analysis.

For continuous secondary outcomes where there no baseline measurement, the two groups will be compared using the unpaired t-test. Alternatively, the Mann-Whitney test will be used if the assumptions of the t-test are not met.

For the continuous outcomes, the exceptions to the previously described methods are for the blood, urine and faecal microbial diversity and metabolomics outcomes. These will be analysed using non-metric multidimensional scaling (NMDS) plots. Additionally, PERMANOVA p-values will be generated using the UniFrac weighted distance matrix generated from Mothur. Family-level extended error bar plots will be generated, White's non-parametric t-test with Benjamini-Hochberg FDR will be utilised.

Binary and nominal outcomes (e.g. achieving diabetes remission) will be compared between the two study groups using either the Chi-square test, or Fisher's exact test if the number of responses in some categories is low.

Ordinal outcomes will be analysed using the Mann-Whitney test to allow for the natural ordering of the response categories.

The secondary efficacy analyses will be performed using the Full Analysis Population.

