4.4 Study Variables

4.4.1 Summary of study data and timing of measurements

The study measured patients at the following timepoints:

- Screening
- Pre-operative mechanistic visit
- Day of the operation

- Early mechanistic post-operative visit 1-2 weeks after operation
- Late mechanistic post-operative visit at 20% total body weight loss of the preoperative value
- 3 months post-operatively
- 6 months post-operatively
- 12 months post-operatively

Table 1 outlines the key study measurements, and the timing of these measurements.

	Screening visit	Pre-op visit	Operation	Early mechanistic post-op visit	Late mechanistic post-op visit	3, 6 months post-op	12 months post-op
Demographics, duration of T2DM	Х						
Weight/weight loss, BMI			х			Х	х
HbA1c			х			х	х
Other blood tests			Х				х
BP /heart rate	х	Х		х	х		х
Body composition and measurements, BMR	x	Х		x	X		х
Comorbidities and King's Score	х						Х
Medications			Х			Х	х
Food diary		Х		Х	Х		
Rates of T2DM remission							Х
Bowel movements							х
GLP-1, GIP, PYY, bile acids, FGFs		Х		X	х		
Fasting Plasma Glucose		Х	x	x	х		х
Postprandial plasma glucose		Х		х	х		
Markers of insulin secretion		Х		х	х		
Ra, Rd, MCR from Clamp		Х		x	х		
VAS		Х		Х	Х		
Microbiota, metabolomics		Х		X	Х		
Faecal calories		Х					х
Adverse events							х

5 Sample Size

The sample size was based on the primary outcome, GLP-1 concentration after the Mixed Meal Tolerance Test.

The study was powered to detect a difference in peak of active GLP-1 of 10.0 pmol/L, equating to the previously estimated change in GLP-1 post-surgery in the Standard Limb RYGB group. The standard deviation of the change in outcome values was estimated to be

10.8 pmol/L within each group. It is calculated that, with a 5% significance level and 90% power, a sample size of 20 patients in each arm was required. Based on experience, it was estimated that up to 20% of patients will drop-out of the study. To allow for this, 25 patients in each arm of the trial were planned, 50 patients in total.

6 Study Objectives and Endpoints

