7.2 Analysis Populations

7.2.1 Full Analysis Population

The Full Analysis Population will consist of patients in the groups to which they were randomised, regardless of deviation from the protocol or whether they received the allocated surgery. Patients with completely missing data at the outcome timepoint will be excluded from this dataset for the particular outcome for which they had missing data.

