7.4 Missing Data

At any timepoint, if there is no data at all for a given outcome, patients with missing data will be excluded from the analysis, and only observed data will be analysed. Missing data will be assumed to be Missing At Random. No imputation procedures will be employed to deal with missing data if it is completely missing at a given timepoint.

During the MTTT, data is collected serially over a short time period. For patients with some data collected, but missing information from the final serial measurements, a Last Observation Carried Forward (LOCF) approach will be used to impute missing data.

[figure not shown]
8 Summary of Study Data

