9.1 Primary Efficacy Analysis

The primary endpoint of the study is the peak of active GLP-1 concentration at the early mechanistic post-op visit.

The analysis will be performed using Analysis of Covariance (ANCOVA). In the analysis, the peak of active GLP-1 concentration at the early mechanistic post-operative visit will be considered as the outcome measure, whilst baseline peak of active GLP-1 will be included as a covariate.

If the data does not meet the assumptions of the ANCOVA analysis (e.g. normally distributed residuals, homogeneity of variance), a data transformation of the outcome variable (e.g. log transformation) before analysis will be utilised to ensure that the assumptions are met.

The summary statistics for the outcome variable will be produced in accordance with section 8.2. The baseline adjusted difference in outcome values between groups will be reported, along with a corresponding 95% confidence interval.

The primary study analysis will be performed using the Full Analysis Population (see section 7.2.1).

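### The 12-month HbA1c and weight comparisons use observed cases one visit at a time, which is valid only under a narrower missing-data assumption than the one the SAP states

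*SAP*

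**What the plan says.** - **Outcomes.** SAP section 6.3.2 lists HbA1c, % total body weight loss and the number of glucose-lowering drugs as endpoints at 3, 6 and 12 months.
- **Method.** Section 9.2 carries the primary ANCOVA over to continuous outcomes that have a baseline, and adds: "The data from each post-operative timepoint will be analysed in a separate analysis". The pattern carried over is that of section 9.1, where "baseline peak of active GLP-1 will be included as a covariate"; no later value enters the model. For continuous outcomes without a baseline, "the two groups will be compared using the unpaired t-test", or Mann-Whitney if its assumptions fail.
- **Missing visits.** Section 7.4: "patients with missing data will be excluded from the analysis, and only observed data will be analysed"; "No imputation procedures will be employed to deal with missing data if it is completely missing at a given timepoint". Section 7.2.1 builds the same exclusion into the Full Analysis Population: "Patients with completely missing data at the outcome timepoint will be excluded from this dataset for the particular outcome".
- **Assumption.** Section 7.4: "Missing data will be assumed to be Missing At Random". It does not say given which variables.
- **Expected loss.** Section 5: "it was estimated that up to 20% of patients will drop-out of the study".
- **Sensitivity analyses.** Section 9.3 has only a per-protocol analysis of the primary outcome. None addresses missing data.

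**The concern.** The stated assumption and the stated method do not match. MAR permits drop-out to depend on anything observed, including a poor 3- or 6-month HbA1c. The 12-month ANCOVA conditions only on arm and baseline, so it needs more than section 7.4 assumes. A patient with values at 3 and 6 months but none at 12 contributes nothing to the 12-month comparison.

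% weight loss is more exposed. It is itself a change from baseline (section 6.4) and has no baseline of its own. Read literally, section 9.2 sends it to a t-test with no covariate, which requires that missingness not depend even on baseline.

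The primary endpoint is a hormone peak at 1-2 weeks. The introduction says the trial will evaluate efficacy on type 2 diabetes, and the later HbA1c and weight results carry much of that message.

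**Working it through.** **1. The plan's figure for loss.** Section 5 needs 20 per arm and allows 20% drop-out: 20 / (1 - 0.20) = 25 per arm, 50 in total. At that ceiling, 0.20 × 50 = 10 patients could lack a 12-month value.

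**2. What each assumption requires.** Write A for arm, B for baseline, Y3, Y6 and Y12 for the visits, and R = 1 if Y12 is observed.
- Observed-case ANCOVA at 12 months needs Y12 independent of R given (A, B).
- MAR with drop-out after 6 months needs only Y12 independent of R given (A, B, Y3, Y6).

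The first can fail while the second holds: it is enough that R depends on Y6, and that Y6 is correlated with Y12 given A and B.

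**3. Assumptions for the size (none is in the SAP).** 25 per arm; 20-22% missing at 12 months, all after a recorded 6-month value; correlation ρ between post-operative visits of 0.5, 0.7 or 0.85; correlation of each with baseline 0.5; logistic drop-out with slope 1 per SD; 6,000 simulated trials per case. The comparator is a likelihood estimate that uses the 3- and 6-month values.

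Bias in the 12-month arm difference (SD units) at ρ = 0.5 / 0.7 / 0.85:

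| Drop-out depends on | Single-visit ANCOVA | Likelihood, all visits |
|---|---|---|
| baseline only | 0.001 / -0.002 / -0.006 | 0.000 / 0.001 / -0.004 |
| 6-month value, same rule in both arms | 0.015 / 0.023 / 0.035 | 0.001 / -0.004 / 0.003 |
| 6-month value, one arm only | 0.052 / 0.091 / 0.117 | 0.004 / 0.002 / 0.000 |
| 6-month value, opposite directions by arm (extreme) | 0.109 / 0.180 / 0.239 | 0.010 / 0.003 / 0.002 |

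For scale, the ANCOVA standard error in the one-arm case is 0.273 to 0.281. The bias is therefore 0.052 / 0.281 = 0.19 to 0.117 / 0.273 = 0.43 of a standard error. With the same rule in both arms it is at most 0.035 / 0.272 = 0.13. The variance of the single-visit ANCOVA relative to the likelihood estimate is 0.99 to 1.18.

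**4. Closed-form check of the one-arm case, no true difference.** Let logit P(drop) = -1.5 + Y6 in one arm and -1.5 in the other, with Z standard normal.
- Drop-out in the first arm: E[expit(-1.5 + Z)] = 0.221. In the other: expit(-1.5) = 0.182. Average: 0.202.
- E[Z × expit(-1.5 + Z)] = 0.148, so the mean 6-month value of those who stay shifts by 0.148 / (1 - 0.221) = 0.190 SD in that arm and by 0 in the other.
- Unadjusted t-test: bias = ρ × 0.190 = 0.095 / 0.133 / 0.162. Simulation: 0.094 / 0.124 / 0.160, with type I error 5.6% / 6.5% / 7.7%.
- Baseline-adjusted: bias ≈ (ρ - 0.5 × 0.5) × 0.190 = 0.048 / 0.086 / 0.114, against 0.052 / 0.091 / 0.117 in the table.

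**5. Shared rule.** With no true difference, both arms shift alike and the bias cancels (within 0.01 SD; type I error 4.8-5.2%). With a true difference of 0.5 SD it is 0.01-0.04 SD, towards zero.

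**The case against.** The case for leaving the plan alone is substantial.

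- **The method is not invalid under every MAR mechanism.** A reader might infer that it is. Section 7.4 names no conditioning variables, and if missingness depends on arm and baseline only, the ANCOVA is unbiased. With complete data, separate analyses by visit are valid. This stands.
- **Interim data are not thrown away.** A reader might infer this too. The 3- and 6-month values are endpoints in their own right and are analysed at their own visits; they go unused only in the 12-month comparison. This stands.
- **The likely effect is small.** With one drop-out rule for both arms, the error is slight and conservative. Other assumed drop-out settings give up to 0.06 SD in that case and 0.17 SD in the one-arm case (35% of a 0.5 SD effect). The SAP gives no slope or correlation to support those figures, and the calculations above give at most 0.12 SD for one-arm drop-out. The trial is described as double-blinded (section 4.1), which makes arm-specific drop-out less plausible without excluding it.
- **The 20% is a ceiling** used to size a 1-2 week outcome, not a forecast for 12 months. Placing all loss after a recorded 6-month value favours the remedy.
- **The reach is limited.** The primary outcome has a single post-operative visit. Diabetes remission is binary and the proposed model does not address it.
- **The t-test for % weight loss is an inference.** The SAP does not assign that outcome by name, and an unadjusted comparison is unbiased under randomisation with complete data.

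These points limit the size and scope. They do not remove the mismatch between sections 7.4 and 9.2, nor the lack of any analysis that would reveal its effect.

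**Conclusion.** The point holds in a limited form. The 12-month ANCOVA on observed cases rests on missingness depending on arm and baseline alone, while section 7.4 states the wider MAR assumption. Where drop-out follows the interim values, bias is about 0 to 0.04 SD if the arms behave alike and about 0.05 to 0.12 SD if only one arm's drop-out follows response. An unadjusted t-test would be somewhat more exposed in the one-arm case.

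These sizes depend on assumed correlations, a drop-out slope of 1 per SD and about 20% missing. They would be smaller with less missing data. The change is worth making because the data are already collected and the remedy is cheap, not because the planned results would be unusable.

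**What to change.** In sections 7.4 and 9.2:

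1. For HbA1c, fit one repeated-measures likelihood model to the 3-, 6- and 12-month values, with arm by visit, baseline by visit and unstructured covariance. Include all patients with any post-operative value. Report the arm difference and 95% CI at each visit.
2. Do the same for body weight, or for % weight loss with baseline weight as covariate, and say so by name so that it does not fall to the unadjusted t-test.
3. Keep the single-visit ANCOVA as a check.
4. State in section 7.4 that MAR is conditional on arm, baseline and the earlier post-operative values.
5. Leave the number of glucose-lowering drugs to a method suited to counts, not a Gaussian model.

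The cost is SAP wording and one extra standard model for each of two outcomes, using software already named in section 11. The model recovers nothing for patients lost before any post-operative visit, and it still relies on MAR.

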4.2 Inclusion-Exclusion Criteria

4.2.1 Inclusion Criteria

The participants must have met ALL of the following criteria to be considered eligible for the study:

- Male or female participants
- Aged between 18-70 years
- Diagnosed with T2DM according to WHO 2006 and 2011 criteria
- HbA1c \geq 7.0% (\geq 53.0 mmol/mol) on screening
- Body mass index (BMI) \ge 30 kg/m² and eligible for bariatric surgery based on NICE guidance
- On glucose-lowering medications
- Willing to comply with study requirements and able to give informed consent

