6.3.2 Secondary outcome measures

The secondary endpoints are measured at several different timepoints.

Endpoints from mixed meal test at late mechanistic post-operative visit:

• Peak of active GLP-1 concentration

Endpoints from both early and late mechanistic post-operative visits:

- a) From the Hyperinsulinaemic Euglycaemic Clamp
 - Rate of glucose appearance (Ra) and disposal (Rd) and metabolic clearance rate of glucose (MCR) basal, low and high
- b) From the MMTT:
 - Active GLP-1 concentration (AUC)
 - Total GLP-1 (peak, AUC)
 - PYY (peak, AUC)
 - GIP (peak, AUC)
 - Markers of insulin secretion (peak, AUC)
 - Plasma glucose (peak, AUC)
 - Bile acids (peak, AUC)
 - FGF-19 and 21 (peak, AUC)
 - Systolic and diastolic blood pressure (AUC)
 - Heart rate (AUC)
 - Appetite ratings (Visual Analogue Scales; AUC)
- c) Blood, urine and faecal microbial diversity and metabolomics
- d) Total caloric intake and macronutrient composition % fat, % protein, % carbohydrates
- e) Body composition and Basic Metabolic Rate (BMR)

Endpoints at the day of surgery:

- Common channel length
- Total small bowel length
- Proportion of common channel to total small bowel length
- Operating time
- Length of in hospital stay

Endpoints at 3, 6 and 12 months:

- HbA1c
- % of total body weight loss
- Number of glucose lowering medications

Secondary endpoints at 12 months:

- % of total body weight loss
- BMI
- Body composition
- Basic Metabolic Rate (BMR)
- Waist, hips and neck measurements
- T2DM remission
- Comorbidities
- Medications
- King's Obesity Staging Score
- Systolic and diastolic blood pressure
- Heart rate
- Oxygen saturation
- Bowel movements frequency

- Blood tests: fasting plasma lipids concentration, fasting plasma glucose, haematinics, vitamins
- Total caloric intake
- Macronutrient composition % fat, % protein, % carbohydrates
- Faecal caloric content

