6.4 Derived values

Peak

For each outcome, the peak will be defined as the maximum post-meal concentration (i.e. from time 15 onwards) per patient, regardless of at which timepoint the peak concentration was achieved.

Area Under the curve (AUC)

A number of outcomes from the mixed-meal tests will be summarised by the Area under the curve values. The AUC will be calculated using the trapezium rule.

For outcomes with measurements at time -30, the first value used in the calculation will be the mean of the -30 and 0 timepoints. When there is no -30 value, the time 0 value will be used as the first measurement in the calculation.

Absolute changes from baseline

Absolute changes from baseline will be calculated by subtracting the individual subject's baseline value from the value at the outcome timepoint.

Percentage changes from baseline

Percentage changes from baseline will be calculated by subtracting the individual subject's baseline value from the value at the outcome timepoint, dividing this sum by the baseline value and multiplying by 100.

7 General Considerations

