8.3 Demographic and Baseline Variables

Baseline values for each parameter are defined as the last value measured before the intervention, i.e. surgery. A summary of patient demographics and baseline measurements are outline in Section 5.4.2.

Descriptive statistics will be produced for these variables for each of the two study arms separately.

The summary statistics will be produced in accordance with section 8.2. No hypothesis tests will be performed to compare the two groups at baseline.

9 Efficacy Analyses

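### Read literally, SAP 9.2 sends percent total body weight loss to an unadjusted test while 12-month BMI, from the same weights, gets ANCOVA; name a baseline covariate for it in advance

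*SAP*

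**What the plan says.** Section 9.2 has two rules for continuous secondary outcomes, apart from the microbial and metabolomic ones.

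- With a baseline: "Secondary outcomes measured on a continuous scale, with a baseline measurement, will be analysed using a similar approach" to that of the primary outcome. In section 9.1 that is ANCOVA with the outcome's own baseline value as covariate.
- Without a baseline: "For continuous secondary outcomes where there no baseline measurement, the two groups will be compared using the unpaired t-test", or Mann-Whitney if the t-test assumptions fail.

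Section 6.3.2 lists the percentage "of total body weight loss" at 3, 6 and 12 months and again in the 12-month list, where BMI also appears. Section 6.4 defines a percentage change as outcome value minus baseline value, then "dividing this sum by the baseline value and multiplying by 100". Section 8.3 defines baseline: "Baseline values for each parameter are defined as the last value measured before the intervention, i.e. surgery". Table 1 in section 4.4.1 has a single row for "Weight/weight loss, BMI". Section 9.2 does not name %TBWL under either rule.

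**The concern.** %TBWL is a change from baseline, so before surgery it is zero for every patient. A covariate that is constant across patients cannot be fitted, so the section 9.1 model cannot be carried over as it stands. What remains in 9.2 is the rule for outcomes without a baseline.

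Twelve-month BMI has a pre-operative value and meets the ANCOVA rule. One set of weights is then analysed in two ways at 12 months, one adjusted and one not, and the two can differ on significance. At all three timepoints %TBWL would also forgo whatever precision the baseline weight could add. If the rule is not read literally, the method and covariate for %TBWL are not fixed at all and could be chosen after the data are seen.

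**Working it through.** **Inputs.** The SAP gives no planning figure for weight, so there is none to reproduce. From section 5, 25 per arm less 20% drop-out leaves 25 × 0.80 = 20 per arm (N = 40). Assumptions, not in the SAP: baseline BMI mean 42, SD 6; %TBWL SD 8; true difference 5 points; r, the correlation of %TBWL with baseline BMI, from 0 to 0.4 (0.5 in one run).

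**Step 1: same data.** Section 6.2 lists height as a baseline characteristic. Taking adult height as fixed,

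BMI at 12 months / baseline BMI = 1 − %TBWL/100.

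The two 12-month endpoints therefore rest on the same two weights per patient.

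**Step 2: precision.** The unadjusted SE of the difference is 8 × √(2/20) = 2.53 points. Adding one covariate multiplies the variance by about (1 − r²) × (N − 3)/(N − 4), here (1 − r²) × 37/36.

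| r | SE ratio, formula | SE ratio, simulated |
|---|---|---|
| 0 | √(1.00 × 37/36) = 1.014 | 1.014 |
| 0.2 | √(0.96 × 37/36) = 0.993 | 0.993 |
| 0.3 | √(0.91 × 37/36) = 0.967 | 0.970 |
| 0.4 | √(0.84 × 37/36) = 0.929 | 0.933 |

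The simulation used 2,500 trials per setting. At r = 0.4, simulated power rises from 49% to 55%.

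**Step 3: chance imbalance.** The between-arm difference in mean baseline BMI has SD 6 × √(2/20) = 1.90 units. The slope of %TBWL on baseline BMI is r × 8/6. A one-SD imbalance shifts the unadjusted %TBWL difference by:

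- r = 0: 0
- r = 0.3: 0.40 × 1.90 = 0.76 points
- r = 0.4: 0.533 × 1.90 = 1.01 points

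These compare with the SE of 2.53.

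**Step 4: validity.** In a second simulation (4,000 trials per setting, 20 or 25 per arm), the t-test on %TBWL rejected in 4.7% to 5.5% of trials with no true difference. Its type I error is sound.

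**Step 5: disagreement at p = 0.05, 12 months, 20 per arm.** As planned means a t-test on %TBWL against ANCOVA on BMI.

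| r | As planned, first simulation | As planned, second simulation | Both adjusted, second simulation |
|---|---|---|---|
| 0 | 7.1% | 6.4% | 4.3% |
| 0.2 | 8.5% | 9.1% | 4.5% |
| 0.3 | 11.7% | 11.0% | 4.4% |
| 0.4 | 14.6% | not run | not run |
| 0.5 | not run | 19.1% | 4.8% |

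A further check of the settings up to r = 0.4 put the both-adjusted figure at about 4% to 6%. With no true difference, disagreement as planned is 1.4% (r = 0) to 4.6% (r = 0.5).

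**The case against.** The strongest reply is that 9.2 never assigns %TBWL to the t-test. Weight has a pre-operative value, 9.2 asks only for a similar approach to the primary, and ANCOVA of %TBWL on baseline weight could be called similar. That reading is available, and the t-test is only what the literal rule yields. But it leaves the covariate (weight or BMI) unnamed, so a clarifying sentence is needed either way.

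Four stronger readings are tempting, and the document does not support them.

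- A reader might infer that the trial's main weight outcome is affected. The SAP ranks no secondary outcome above another.
- A reader might infer that baseline weight is ignored and that chance imbalance passes straight into %TBWL. Baseline weight is already the denominator, and imbalance enters only through r, which the SAP does not give.
- A reader might infer that the t-test is wrong. It is valid under randomisation.
- A reader might infer duplicate results at every visit. BMI is a listed endpoint only at 12 months.

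It is also fair that the disagreement figures are not all due to the missing adjustment. About 4% to 6% remains when both outcomes are adjusted, because one is a percentage and the other an absolute value. The 5-point scenario has power near 50%, where results near p = 0.05 are common.

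**Conclusion.** The point stands as a minor one about efficiency and consistency in a secondary outcome. Under the literal rule in 9.2, %TBWL gets an unadjusted test and 12-month BMI gets ANCOVA, although both come from the same weights.

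Under the stated assumptions at 20 per arm, adjustment costs about 1% in SE if baseline is unrelated (r = 0), and gains about 3% at r = 0.3 and 7% at r = 0.4. It would cut disagreement between the two 12-month analyses from about 7–15% to about 4–6% of trials. Because r is not documented, a material loss of precision is possible but not shown. Neither the primary analysis nor the validity of the %TBWL comparison is in question.

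**What to change.** Add one sentence to section 9.2: percent total body weight loss at 3, 6 and 12 months is analysed by ANCOVA with baseline weight as covariate, each timepoint separately. Baseline BMI would also serve, but one of the two should be named in advance. Record the change and its reason as section 12.4 provides, before outcome data are seen by arm.

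The cost is one degree of freedom, about 1% wider SE if baseline proves unrelated, and no new data. Listing %TBWL only once in section 6.3.2, or reporting 12-month BMI descriptively, is optional and not needed to settle this point.

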9.4 Other Analyses

An additional set of analyses will examine the association between the key primary and secondary efficacy outcomes measured on a continuous scale and the proportion of the common channel length to the total small bowel length. The analysis will be performed using Pearson correlation. Alternatively, Spearman's rank correlation will be used if the Pearson correlation assumptions (e.g. non-linear relationship, both variables non-normally distributed) are not met. For each outcome, a single analysis will be performed for all patients, combining the two study arms together.

10 Safety Analyses

The main safety outcome is the occurrence of adverse events (AEs). For each of the study groups, the number of adverse events in each group and per patient will be summarised. Specific details of the adverse events will be recorded in addition to the number of AEs that are serious and non-serious.

If it is deemed that there are sufficient occurrences of adverse events in total, a formal test of significance will be performed to compare AE occurrence at the patient level between study arms. Fisher's exact test will be used for this analysis. However, it is acknowledged that the study is unlikely to be powered to show a difference between groups for this endpoint.

11 Technical Details

The data analysis will be primary performed using the statistical software packages Stata (version 15.1), SPSS (version 20 or later), GraphPad PRISM (version 6 or later). Programs recording details of all data manipulation and data analyses will be produced and kept, so that the analyses can be externally inspected and, if necessary, re-run.

The exception is for the analysis of the blood, urine and faecal microbial diversity and metabolomics outcomes, which will be analysed using the Vegan library within the R statistical package and the Statistical Analysis of Metagenomic Profiles software package.

12 Summary of Changes to the Analysis Plan

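### SAP section 9.2 gives metabolomics a phylogenetic distance and a taxonomic feature level that cannot be computed on metabolites, and does not state the contrasts or how pre-operative samples enter

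*SAP*

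**What the plan says.** SAP section 6.3.2 lists "Blood, urine and faecal microbial diversity and metabolomics" as a secondary endpoint at both the early and the late mechanistic post-operative visits. The row "Microbiota, metabolomics" in Table 1 (section 4.4.1) is marked at the pre-operative visit as well as at those two visits.

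Section 9.2 sets a general rule: "Secondary outcomes measured on a continuous scale, with a baseline measurement, will be analysed using a similar approach to that outline for the primary efficacy" analysis, that is, ANCOVA with the baseline value as covariate. It then says that "the exceptions to the previously described methods are for the blood, urine and faecal microbial diversity and metabolomics outcomes". For this excepted group it gives three instructions:

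- on ordination, "These will be analysed using non-metric multidimensional scaling (NMDS) plots";
- on the overall test of the profiles, "PERMANOVA p-values will be generated using the UniFrac weighted distance matrix generated from Mothur";
- on the display and testing of single features, "Family-level extended error bar plots will be generated, White's non-parametric t-test with Benjamini-Hochberg FDR will be utilised".

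Section 11 keeps the same grouping. It says that all of these outcomes will be "analysed using the Vegan library within the R statistical package and the Statistical Analysis of Metagenomic Profiles software package". Neither section names any other distance, feature unit or test for metabolomics.

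**The concern.** UniFrac measures how far apart two communities of organisms are on a phylogenetic tree, and family is a rank in a taxonomy. Both suit sequencing data. Neither has a meaning for metabolite intensities in blood, urine or faeces. Section 9.2 nevertheless applies them to a group that includes metabolomics, after removing that group from the rules that could have served instead.

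The same paragraph leaves the comparison itself open. It does not say whether the tests are between arms or between visits, which terms enter PERMANOVA, or what the pre-operative sample is for. Two analysts could follow the text faithfully and test different hypotheses. For metabolomics they would also have to choose the distance, the feature unit and the set of tests over which the false discovery rate is controlled. With many features and two post-operative visits, that is a good deal of freedom in an endpoint meant to help explain the mechanism.

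**Working it through.** The plan gives no figure on this point, so there is none to reproduce. The check sets each prescribed element against the data it needs.

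| Element in section 9.2 | What it needs | On metabolite profiles |
|---|---|---|
| NMDS plot | A distance between samples | Can run, but no usable distance is named |
| PERMANOVA on weighted UniFrac | Taxon abundances and a phylogenetic tree | PERMANOVA can run; this distance cannot be computed |
| Family-level error bar plots | A taxonomic assignment of each feature | Cannot be produced |
| White's test with Benjamini-Hochberg | Two groups and a defined list of features | Can run, but no metabolite feature list is defined |

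**Can another rule in the SAP fill the gap?** No. ANCOVA, the t-test and the Mann-Whitney test for continuous outcomes come before the exception clause, and that clause removes these outcomes from them. Section 11 adds only software, and the same software for both data types.

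**Does a narrower reading help?** Suppose UniFrac and family level were meant for the microbiota alone. Metabolomics then keeps NMDS plots on an unnamed distance and, at most, White's test on unnamed features. It still has no executable pre-specified distance or feature-level test.

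**Pre-operative samples.** Table 1 schedules them, so a baseline exists in the sense of section 8.3 (last value before surgery). Other continuous secondary outcomes with a baseline get ANCOVA. The excepted outcomes do not, and nothing is said in its place. White's test compares two groups and has no place for a covariate. PERMANOVA could carry a baseline or time term, but no terms are given.

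**What baseline adjustment could be worth.** For one continuous feature under a linear model with pre/post correlation ρ, residual variance after adjustment is 1 − ρ² of the unadjusted variance. The SAP gives no ρ, so the values below are assumptions.

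- ρ = 0.3: 1 − 0.09 = 0.91, a cut of 9%
- ρ = 0.5: 1 − 0.25 = 0.75, a cut of 25%
- ρ = 0.7: 1 − 0.49 = 0.51, a cut of 49%

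These figures apply to single features such as one log metabolite intensity. They say nothing about the power of PERMANOVA.

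**The case against.** The best defence is that the intention is plain: UniFrac and family level belong to the sequencing data, and NMDS, PERMANOVA and White's test with Benjamini-Hochberg all work on a metabolite matrix once a distance and features are supplied. That is correct. A reader who infers that none of the named methods can be used for metabolomics goes too far. What is missing is the distance and the feature unit, and the defence does not supply them.

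A reader might also infer that the plan ignores the pre-operative samples. The SAP does not say so. It is silent on contrasts and model terms, and PERMANOVA can include a baseline term. An unadjusted comparison between randomised arms is also valid; it costs precision and does not bias the result. For sparse family abundances, keeping a non-parametric test in place of ANCOVA is a defensible choice.

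A third inference is that visits will be pooled with free permutation, so that p-values come out too small. Nothing in the SAP pools visits. Section 9.2 has a rule that each post-operative timepoint is analysed separately. Whether the exception clause displaces that rule is unclear, but no text puts pooling in its place. The direction of error would also depend on the contrast: ignoring positive within-patient correlation usually makes p-values too large for a comparison between visits.

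Finally, section 12.4 says later revisions will be documented with reasons, so a choice made after seeing the data is a risk and not a certainty. Documentation alone does not remove that risk unless the revision is made before these data are examined.

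**Conclusion.** The point holds in a limited form. Section 9.2 states a rule that fails for part of the endpoint it covers: the only distance and the only feature level it names cannot be computed for metabolomics. This conclusion rests on the wording of sections 9.2 and 11 and on what the two methods require, and on no numerical assumption. It survives the charitable reading, which leaves metabolomics with plots but without a specified distance or feature unit.

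The second part is an omission: the contrasts and the role of the pre-operative samples are not stated. The documents do not support the stronger claims that those samples are discarded or that repeated samples are treated as independent. The possible gain in precision is 9% to 49% of residual variance per continuous feature, over assumed correlations of 0.3 to 0.7.

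The impact is confined to one secondary mechanistic endpoint. The plan should be corrected, but the primary analysis does not depend on it.

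**What to change.** Split the paragraph in section 9.2 in two, and adjust section 11 to match.

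- **Microbiota.** Keep PERMANOVA on weighted UniFrac and the family-level tests with Benjamini-Hochberg. State that both compare the two arms at each post-operative visit separately. If any model includes several visits, restrict the permutations so that each patient's samples stay together. State what the pre-operative samples are used for, even if only for description.
- **Metabolomics.** Use ANCOVA for each metabolite on log intensity, with the pre-operative value as covariate, in line with the rule for other continuous secondary outcomes. Apply Benjamini-Hochberg within each fluid. For the overall profile, use PERMANOVA on the Euclidean distance of log-transformed, scaled profiles, between arms at each visit. Name this one distance and leave no alternatives.

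The cost is one rewritten paragraph and a matching line on software. Vegan already covers PERMANOVA, and the per-metabolite ANCOVA is ordinary linear modelling. No new samples or visits are needed. The revision should be dated and made before the microbiota and metabolomics data are examined by arm. If that is no longer possible, the metabolomics analysis should be reported as not pre-specified.
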